### **9.1 STUDY DESIGN**

Data extraction from both databases (I and II, see [section 9.4](#)) will be conducted by

. All patients will be required to have a prescription for ICS/LABA therapy [e.g. Advair (Diskus and HFA), Airduo, Breo, Dulera, or Symbicort]. The date of the first prescription of ICS/LABA within the study period (Jan 1st 2016 to Nov 30th 2018) will be defined as ICS/LABA-initiation (ICS/LABAi) date. This baseline cohort will then be followed to identify two cohorts (two arms of the study). One cohort that receives a prescription for Tiotropium Respimat® 1.25 mcg (on top of baseline ICS/LABA) will be classified as the ‘Tio’ group, and the second cohort that receives a “step-up” from baseline low-dose ICS/LABA to medium/high dose ICS/LABA or from baseline medium dose ICS/LABA to high dose ICS/LABA or an additional prescription/refill of high-dose-ICS/LABA following the first prescription of baseline high dose ICS/LABA within the study period, will be classified as the ‘NonTio’ group. The date of the first prescription for Tiotropium Respimat® 1.25 mcg in the ‘Tio’ group will be defined as the index date for the ‘Tio’ group. Similarly the date of the first prescription for a “step-up” from baseline low-dose ICS/LABA to medium/high dose ICS/LABA or from baseline medium dose ICS/LABA to high dose ICS/LABA or an additional prescription/refill of high-dose-ICS/LABA following the first prescription of baseline high dose ICS/LABA (evidenced by at least 90-days of prescription utilization) within the study period will be defined as the index date for the ‘NonTio’ group.

Patients will be required to have a minimum follow-up period of 30 days after the index date for the analyses of the primary endpoint with no limit on the maximum period (this 30-day minimum follow-up period requirement will be waived in a sensitivity analysis). Subject to sample size requirements, patients will be required to have available records for at least 12 months prior to the index date to ensure no prior use of Tiotropium Respimat® and to establish baseline patient characteristics. This 12-month period prior to the index date will be defined as the pre-index period.

Figure 9.1.1 Study Design

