**Table 1: Matching Parameters**

Variable Name and Type	Description	Applicable to Study Cohort: 1=IMS, 2=EMRClaims+
ICS/LABA dose on ICS/LABAI date	The dose level of the first prescription on the ICS/LABAI date (low, medium, or high)	1 and 2
Demographics (categorical and continuous variables)	Age (10-year increments) and Gender Male/Female), Region (if available, Northeast, Midwest, South, West)	1 and 2
CCI (continuous variable)	Charlson Comorbidity Index score	1 and 2
Specific comorbidities (categorical variables)	Cardiovascular conditions, cerebrovascular diseases, hypertension, diabetes, metabolic and endocrine comorbidities, anxiety and depression, gastro-esophageal reflux disease, cancer and obesity identified using appropriate ICD codes. All above measures will be coded as binary (yes/no) variables.	1 and 2
Medications (categorical variable)	Polypharmacy level matched within a range of 2 drugs (for example, 0-2,3-5,6-8,8-10 and so on).	1 and 2
Asthma Control Status: Well Control or Poor Control (categorical variable)	‘Well Controlled’ if patient has no prescriptions for an OCS, and no asthma-related emergency department visits or hospitalizations other than the first diagnosis recorded in the data extracted (Ref: Stempel JACI 2005). Categories will include Well Controlled and Not Well Controlled.	1 and 2
Hospital admissions Outpatient visits ER visits and OCS use (categorical variables)	Poorly Controlled patients (“Not Well Controlled”) will further be matched based on the presence of asthma-related admissions, outpatient visits, and ER visits or use of OCS during the pre-index period.	1 and 2
Eosinophil levels (EMRClaims+ database only) (categorical variables)	Eosinophil level categories: <150 cells/μL, 151-300cells/μL, 301-400 cells/μL, ≥400 cells/μL (as available)	2
Asthma Control Test (ACT) results (EMRClaims+ database only) (categorical variables)	ACT score categories developed based on data distribution (as available)	2

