## 9.12 BIAS

### Channeling Bias Mitigation

Introduction of channeling bias in this study is highly likely using retrospective claims data based on asthma medication use; patients between the two cohorts may differ in baseline control and severity levels. On aggregate, patients for whom Tiotropium Respimat® 1.25 mcg was added (vs NonTio) are likely to be less well-controlled and more severe both at baseline and during the follow up period. Absent a method to control for this channeling bias, it is likely that placing sicker patients in the Tiotropium Respimat® 1.25mcg group will confound an accurate comparison of cost, resource use, and other outcomes between the groups. Two design features of our study will help mitigate this bias. First, our comparison (NonTio) group will be required to step-up their baseline ICS/LABA dose or have an additional prescription/refill of high-dose-ICS/LABA following the first prescription of baseline high dose ICS/LABA within the study period. Second, we will use Propensity Score Matching (PSM) to match patients on key measures of disease control and severity as listed in [Table 1](#), such as demographics, Charlson Comorbidity Index (CCI) score, specific comorbidities, number of prescriptions (overall and asthma-related medications). This baseline matching strategy will be particularly important to ensure that patients in the TIO group who have a corresponding increase in their ICS dose at or prior to the date of their TIO prescription (for example, if the patient has an exacerbation), will be matched to a corresponding NonTIO patient in terms of increased ICS dose or additional ICS prescription. It should be noted that after the prescription index date for both Tio and NonTio patients, we anticipate changes in ICS medication for patients in both cohorts. These ICS medication changes reflect patient

outcomes in the follow-up period, where patients who encounter exacerbation in either group are likely to see a change in the ICS dose.

As a result, post-index period ICS medication changes will not alter the classification of patient groups nor will it be the basis for exclusion of these patients.

We will conduct 1:2 matching using a nearest neighbour matching approach with a radius of  $0.2 * SD(\log(P))$ . This will be conducted in both databases (IMS: Cohort I and EMRClaims+: Cohort II) separately.

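### The single primary HR pools step-up and high-dose refill comparators under a dose-increase label, and section 9.12 credits Table 1 with matching variables that it does not contain

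*Combined protocol and SAP*

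**What the plan says.** Section 8 sets tiotropium add-on against a rise in ICS dose, and section 9.7.1 describes the treatment term of the primary Cox model in the same terms. Section 9.1 defines the NonTio group more widely. It takes patients who step up from a low or medium initial ICS/LABA dose, and also patients who have "an additional prescription/refill of high-dose-ICS/LABA following the first prescription of baseline high dose ICS/LABA". Section 9.9 acknowledges that including the second kind makes the results harder to interpret.

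Section 9.12 offers two protections against channeling: the NonTio entry rule and propensity score matching. The matching is to "match patients on key measures of disease control and severity as listed in" Table 1, and the examples given include "number of prescriptions (overall and asthma-related medications". It is described as particularly important so that "patients in the TIO group who have a corresponding increase in their ICS dose at or prior to the date of their TIO prescription" "will be matched to a corresponding NonTIO patient in terms of increased ICS dose or additional ICS prescription". The method is 1:2 nearest neighbour with a radius of 0.2 SD, and "This will be conducted in both databases (IMS: Cohort I and EMRClaims+: Cohort II) separately".

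Table 1 has one ICS dose row: "The dose level of the first prescription on the ICS/LABAI date (low, medium, or high". Its medications row is "Polypharmacy level matched within a range of 2 drugs". OCS use also appears, as presence or absence, in the control-status definition and in the further matching of patients who are not well controlled.

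**The concern.** Two things do not fit together.

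First, the label and the comparator differ. A NonTio patient with a high initial dose has had no dose increase, but contributes to an HR described as tiotropium against a dose increase. If balance is achieved, section 9.7.1 limits the model to database and treatment, so the report would carry one HR and no estimate against step-up alone, which is the contrast in the objective.

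Second, section 9.12 relies on Table 1 for content that is not there. A programmer who builds the score from Table 1 will have no asthma-related prescription count and no variable for an ICS increase between the first ICS/LABA prescription and the index date. Section 9.12 itself calls channeling highly likely, so its account of the matching should agree with the matching list.

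**Working it through.** **1. Section 9.12 against Table 1.**
- Number of prescriptions overall: Table 1 has a banded count of drugs. Broadly covered.
- Number of asthma-related prescriptions: no row. OCS use is recorded as presence only.
- ICS increase at or before index: no row. There is no dose at index, no change from initial dose and no step-up flag.
- Initial ICS/LABA dose: present, as one term in the score; exact matching is not stated.

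**2. What initial dose tells us.** Under section 9.1, a NonTio patient with a low or medium initial dose has stepped up, and one with a high initial dose has refilled. Initial dose therefore identifies comparator type on the NonTio side. It does not show whether a Tio patient's ICS rose before index.

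**3. Why one HR is not enough.** Take PRIMO-based rates over 11 months and a true HR of 0.80 against step-up. Let the refill rate be 0.0224 divided by an assumed HR against refill, and let the pooled HR be the ratio of events per person-month. If 50% of NonTio are refillers and the HR against refill is 1.00, the pooled HR is about 0.89. If 25% are refillers and the HR against refill is 1.25, it is about 0.88. With no refillers, a pooled 0.89 would itself be the step-up HR. One pooled figure cannot tell these cases apart. The refill shares and refill HRs are assumptions, and an HR against refill below 0.80 would move the pooled value the other way.

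**4. Precision of separate HRs.** Inputs from section 9.5: 2,100 Tio and 4,200 NonTio; monthly rates 0.0096 and 0.012 (MEZZO-based) or 0.0224 and 0.028 (PRIMO-based); HR 0.80 in both.

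Events per arm = N × (1 − exp(−rate × months)); SE(log HR) = √(1/d0 + 1/d1), where d0 and d1 are NonTio and Tio events; 95% CI = 0.80 × exp(±1.96 × SE).

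Plan's own figures first, with two-sided 5% assumed: PRIMO rates over 11 months give 98% power, as stated. MEZZO rates give 50% at 5.5 months and 78% at 11 months, against the stated 77%. The 5.5 months may serve only to derive the rate, and section 9.1 sets no maximum follow-up, so the 77% is not shown to be wrong. Both lengths are carried forward.

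| Setting | Events (NonTio + Tio) | SE, all sets | CI, all sets | CI, half the sets | CI, a quarter |
|---|---|---|---|---|---|
| MEZZO, 5.5 months | 268 + 108 | 0.114 | 0.64–1.00 | 0.58–1.10 | 0.51–1.25 |
| MEZZO, 11 months | 519 + 210 | 0.082 | 0.68–0.94 | 0.64–1.00 | 0.58–1.10 |
| PRIMO, 11 months | 1,113 + 459 | 0.055 | 0.72–0.89 | 0.69–0.93 | 0.64–0.99 |

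Halving the sets multiplies the SE by √2 (0.161, 0.116, 0.078); quartering doubles it (0.228, 0.163, 0.111).

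**5. Why match exactly on initial dose.** The documents give no dose mix, NonTio pool size or split of Tio patients by database, so a simulation rests wholly on assumed inputs: 100, 300 or 2,000 Tio patients per database; a NonTio pool 3, 5 or 10 times as large; four dose mixes; ten other covariates shifted by 0.1 or 0.2 SD; greedy 1:2 matching without replacement and a 0.2 SD caliper.
- When sets were split by the Tio patient's initial dose, about 1% to 40% of comparators in the low/medium sets were refillers under score-only matching, and 0% under exact matching.
- Exact matching moved the refiller share of the whole NonTio arm by at most 1.7 percentage points.

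Exact matching thus serves the separate HRs and is not expected to change the overall HR materially.

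**The case against.** The pooled comparator is an open design choice. It is defined in section 9.1, repeated in 9.3.1 and 9.12, and its difficulty is conceded in 9.9, which also says that no effectiveness claim should rest on the study. Nothing is concealed, and no stratified HR was promised. That stands, but disclosure supplies no estimate, and sections 8 and 9.7.1 still carry the dose-increase label.

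A reader might infer that section 9.12 is plainly breached. It is not: its promise is met by an increased dose or an additional prescription, and every NonTio patient satisfies one or the other through entry. That a stepped-up Tio patient must be paired with a stepped-up NonTio patient is a stricter promise than the text makes. What remains is that the matching variables are not what secures it, although 9.12 says they do.

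A reader might also infer that the matching does nothing about comparator type. The documents do not support that: initial dose is in Table 1, and 9.7.1 adds any unbalanced characteristic to the model. Control is partial rather than absent.

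Finally, the list in 9.12 is illustrative, and section 9.4 leaves covariates open to finalisation. Both permit a correction; neither makes one.

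**Conclusion.** The point holds as a matter of interpretability and internal consistency. The primary HR combines tiotropium against step-up with tiotropium against continued high dose. Only the first is the stated objective, and no planned analysis shows it alone. Section 9.12 also attributes to Table 1 an asthma-related prescription count and a basis for matching on ICS increase that the table lacks. It should be fixed, and is easily fixed.

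It is tempting to conclude that the overall HR is biased, or biased in one direction. The documents do not support that: they give neither the share of refillers nor an HR against them. The textual findings depend on no calculation. The precision figures rest on the section 9.5 rates and sample size and on an assumed share of sets in each stratum; the matching figures rest on assumed inputs throughout.

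**What to change.** 1. Keep the overall HR as primary. Pre-specify in 9.7.1 the HR with 95% CI separately for low/medium initial dose (Tio against step-up) and high initial dose (Tio against refill), as estimates and not further tests. Match exactly on initial dose level within each database so that the strata stay matched. Because comparator type and initial dose coincide in NonTio, a difference between the two HRs should not be attributed to comparator type alone.
2. In sections 8 and 9.7.1, label the overall contrast as Tio against step-up or continued high-dose ICS/LABA.
3. Add the asthma-related prescription count to Table 1, as 9.12 already implies, and reconcile the assurance in 9.12 with what Table 1 contains. Report descriptively how many Tio patients had an ICS increase at or before index. A further HR by that split is not proposed, because its precision has not been worked out and could be poor.

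The work is wording plus derivations from prescription data already used to classify patients. The price is the wider stratum intervals tabulated above and some lost matches, mainly in the smaller database. On the assumed simulation inputs, the share of Tio patients with two matches fell by roughly 1 to 9 percentage points with 100 Tio patients, 0.1 to 3.8 with 300, and at most 0.7 with 2,000.

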## 9.3 VARIABLES

### 9.3.1 Exposures

The exposure variables in this study include Tio initiation, and ICS/LABA dose increase or an additional prescription/refill of high-dose-ICS/LABA following the first prescription of baseline high dose ICS/LABA for at least 3 months.

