## **9.6 DATA MANAGEMENT**

All established security and confidentiality procedures will be observed by BI and/or personnel who are assigned appropriate access to the data. Enrolment data, medical claims, and prescription claims will be accessed from this administrative claims dataset. The analyses will be performed on limited data sets that are void of member protected health information and all results were shared in aggregate form only.

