## **9.9 LIMITATIONS OF THE RESEARCH METHODS**

Claims and EMR data are subject to certain limitations. The presence of a claim for a filled prescription or prescription absent a claim does not indicate that the medication was consumed or that it was taken as prescribed, and any medications filled over-the-counter or provided as samples by the physician will not be observed in the claims data. Finally, as with all claims-based analyses, study results may not be generalizable to the overall population as patients who have commercial health insurance may be different from those with non-commercial or without (commercial) health insurance. Database I underrepresents the population aged 65 years and older, which may affect external validity in the case of Medicare, Medicare Advantage or Medicaid patients. Since unmatched patients will be excluded, the results may not be generalizable to all patients. Some study measures and outcomes will include missing data and hence reduce the sample size. Not all patients in Database II will have lung function results or ACT scores, therefore, the sample size for related secondary endpoints or sub-group analyses may produce results for these analyses that are not generalizable. While duplication analyses will make double counting the same patient across both datasets negligible, it should be noted that the same patient may be present in both cohorts.

Including patients with persistent use of high-dose ICS/LABA (as opposed to an increase in ICS/LABA dose) in the NonTio group, may complicate the interpretation of the results, as patients with a deterioration in their asthma necessitating an increase in asthma medication (Tio group) will be matched to patients continuing on the same medication (high-dose ICS/LABA).

No claims regarding the effectiveness of Tio should be made on the basis of this study. This real-world evidence study lacks controls available with randomized controlled trials. Patient misclassification, missing data, objective and reliable measurement of patient outcomes, and lack of detailed information regarding subjects' clinical history or clinical status during the study timeframe may undermine the accuracy of our study results.

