## 9.11 SUBJECTS

1. Patients with least one asthma diagnosis in the inpatient setting or at least two separate instances of asthma diagnosis (separated by at least 30 days) recorded in the outpatient or emergency room setting will be included (ICD 9 CM: 493.xx or ICD 10: J45-J45.999).
2. Patients will be required to be already on ICS/LABA.
3. Patients below the age of 6 years on the ICS/LABAI date will be excluded.
4. Patients will be required to have available records 12 months prior to the index date (6 months will be used if patient exclusions due to this criteria adversely affect the study sample size).
5. Patients with a diagnosis of COPD at any time during the study period will be excluded.
6. Those who are on biologics at baseline will be removed.
7. After the PSM process, unmatched patients will be excluded.

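### Table 1 has no measure of how regularly ICS/LABA was filled before index, so prior coverage may differ between Tio and NonTio and may confound the hazard ratio

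*Combined protocol and SAP*

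**What the plan says.** **Matching variables.** For ICS/LABA, Table 1 lists "The dose level of the first prescription on the ICS/LABAI date (low, medium, or high"). The other drug items are "Polypharmacy level matched within a range of 2 drugs" and, for patients who are not well controlled, OCS use. It has no days covered, number of ICS/LABA fills, refill gap or duration of use.

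**Section 9.12** describes the matching differently. It says the Table 1 measures include counts of prescriptions, both in total and for asthma drugs. It adds that Tio patients whose ICS dose rose at or before index will be matched to NonTio patients on a dose increase or an extra ICS prescription.

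**Entry to NonTio.** Section 9.1 requires a step-up in ICS/LABA dose or a further high-dose prescription or refill, "evidenced by at least 90-days of prescription utilization". Section 9.3.1 gives the corresponding exposure as "an additional prescription/refill of high-dose-ICS/LABA following the first prescription of baseline high dose ICS/LABA for at least 3 months". Neither says whether this period lies before or after index.

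**Entry to Tio.** Under section 9.1 a Tio patient "receives a prescription for Tiotropium Respimat® 1.25 mcg (on top of baseline ICS/LABA"). The common requirement in section 9.11 is "Patients will be required to be already on ICS/LABA". Neither sets a number of fills or a duration.

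**Analysis.** Under section 9.7.1, if matching balances the observed characteristics, the outcome models contain only database and treatment.

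**Data.** Section 9.6 states "Enrolment data, medical claims, and prescription claims will be accessed". Section 9.9 notes in general terms that a claim "does not indicate that the medication was consumed or that it was taken as prescribed"; it does not discuss a difference in prior filling between the arms.

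**The concern.** A patient who filled ICS/LABA once and a patient who filled it every month have the same Table 1 dose entry and can have the same drug count. The propensity score cannot tell them apart.

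That would matter less if both arms were chosen in the same way, but they are not. The NonTio index date is itself an ICS/LABA prescription or refill, so each NonTio patient is being supplied with ICS/LABA at that moment. The Tio index date is a tiotropium prescription, and no rule excludes a patient whose ICS/LABA supply has lapsed.

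If fill regularity also predicts exacerbation, the hazard ratio would partly compare regular with irregular ICS/LABA users. The planned balance check would not show this, because the variable is not among those checked, and the outcome model would not adjust for it.

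**Working it through.** The plan states no figure on adherence, so there is none to reproduce. The check has two parts.

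**1. The entry rules side by side**

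| Feature | NonTio | Tio |
|---|---|---|
| Index event | Step-up in ICS/LABA, or further high-dose prescription/refill (9.1) | First tiotropium prescription (9.1) |
| Further ICS/LABA prescription or fill needed by index | Yes, by definition | No |
| Minimum ICS/LABA use | 90 days or 3 months, at least on the high-dose refill route (9.1, 9.3.1) | None stated (9.1, 9.11) |
| Fill regularity in Table 1 | Absent | Absent |

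The difference in the second row does not depend on where the 90 days fall. The third row does. If the 90 days run past index, they select on later persistence, which is a separate problem.

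**2. Illustration of size, in both directions**

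The planned hazard ratio follows from section 9.5: 0.0096 / 0.012 = 0.80. Everything else here is assumed, because the documents give no adherence data.

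- pT, the share of regular fillers in Tio after matching: 40-50%.
- pN, the same share in NonTio: 60-80%.
- r, the hazard ratio for regular versus irregular fillers: 0.6-0.8 if regular filling is protective, 1.25-1.5 if it marks more severe disease.

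Bias factor b = (pT·r + 1 − pT) / (pN·r + 1 − pN). Apparent HR = 0.80 × b. This simple mixture of hazards ignores changes in the mix over follow-up.

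| r | pT | pN | b | Apparent HR |
|---|---|---|---|---|
| 0.8 | 0.5 | 0.6 | 0.90/0.88 = 1.023 | 0.82 |
| 0.6 | 0.4 | 0.8 | 0.84/0.68 = 1.235 | 0.99 |
| 1.25 | 0.5 | 0.6 | 1.125/1.15 = 0.978 | 0.78 |
| 1.5 | 0.4 | 0.8 | 1.20/1.40 = 0.857 | 0.69 |

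These are the extremes of the grid in each direction. A milder protective set takes low coverage in 50-60% of Tio and 30-40% of NonTio, with a hazard ratio of 1.2-1.3 for low versus good coverage. It gives b from 1.10/1.08 = 1.019 to 1.18/1.09 = 1.083, so 0.80 appears as 0.82 to 0.87. If pT = pN, b = 1 and there is no bias.

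**The case against.** **Section 9.12 promises more than Table 1 shows.** Prescription counts for asthma drugs, and matching on an additional ICS prescription, would partly stand in for fill history. A reader who looks only at Table 1 might infer that no proxy was ever intended, and that would be wrong. But section 9.12 attributes the counts to Table 1, and they are not there, so it is unclear whether they will be used. Matching on an additional prescription concerns an escalation event rather than regularity.

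**A count over a fixed 12-month pre-index period has a fixed denominator.** This is fair, and such a count would help. It remains partial: the same number of fills is full coverage for someone who started shortly before index and sparse coverage for someone who started a year before.

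**Poor fillers can enter either arm.** This stands. A patient who fills irregularly and looks uncontrolled may be stepped up into NonTio as readily as given tiotropium. The share of NonTio entering by high-dose refill is not given. If only that route differed, the gap across the arm would be that share multiplied by the gap within the route. Matching on dose, control status, asthma-related visits and OCS may reduce it further.

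**The plan is cautious and leaves room for change.** Section 9.9 warns about including persistent high-dose users and bars effectiveness claims from this study. Section 9.4 leaves covariates open until the data have been evaluated. Neither names differential prior filling, though section 9.4 makes the amendment easy.

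**Conclusion.** The point holds as a gap in the matching set that should be closed before analysis, with low confidence about its effect. Two things are certain: Table 1 has no ICS/LABA fill-regularity measure, and Table 1 and section 9.12 disagree about prescription counts. The entry rules give a concrete reason why coverage may differ between the arms.

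A reader might infer three stronger conclusions that the documents do not support:

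- *That adherence is confounded with treatment.* No adherence data are given, and the position of the 90-day window is not stated. Only that it may be confounded can be said.
- *That the bias works against Tio.* The illustration runs both ways, with 0.80 appearing as 0.82-0.99 or as 0.78-0.69 depending entirely on assumed values.
- *That a definite amount of power is lost.* With direction and size both unknown, no power figure can be defended.

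**What to change.** Add a row to Table 1 for databases 1 and 2: *Pre-index ICS/LABA proportion of days covered, from the first ICS/LABA fill in the pre-index period to the day before index (for example <50%, 50-79%, ≥80%).* Enter it in the propensity model and report it in the balance table before and after matching. Wording it by pre-index period keeps it valid if the 6-month option in section 9.11 is used.

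Reconcile Table 1 with section 9.12: either list the prescription counts and the additional-ICS-prescription item in Table 1, or remove them from section 9.12.

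Separately, state where the 90-day (or 3-month) window lies relative to index and to which NonTio routes it applies. A pre-index covariate does not correct selection on persistence after index.

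The cost is one variable derived from prescription claims already being accessed, plus a few lines of text. There are two downsides: the measure is imprecise when index soon follows the first fill, and Tio patients with low coverage may have fewer NonTio matches. If coverage turns out balanced, the balance table will show it.

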## **7. RATIONALE AND BACKGROUND**

While asthma imposes a substantial burden on the healthcare system, the cost of uncontrolled asthma is more than double that for controlled asthma patients (ACAAI). The European National Health and Wellness Survey ([P19-00715](#)) and the Real-world Evaluation of Asthma Control and Treatment (US) ([R16-0701](#)) survey both found that 55% of asthma patients were uncontrolled, even among those who are treated. Asthma therapy involves a stepwise approach depending on control and severity levels. Uncontrolled asthma, which may present regardless of severity level, results in exacerbations, use of systemic corticosteroids, and declined lung function ([P14-03600](#)). When asthma is not controlled, guidelines recommend increased ICS dose, and use of ICS in combination with long-acting  $\beta$ 2-agonists (LABA), and/or other add-on therapy, including leukotriene receptor antagonists (LTRA), antibody biologics or oral corticosteroids. The ERS/ATS guidelines ([P14-03600](#)) define severe asthma as that which remains uncontrolled despite use of high dose ICS as well as controller medications or systemic corticosteroids. Uncontrolled asthma is associated with an increased risk of exacerbation, which results in impaired lung function, reduced patient quality of life and increased health care resource use. To better guide treatment decision making, it is imperative to understand the impact of different treatment choices on health outcomes in a real-world setting for patients taking ICS/LABA combinations.

The intended audience will be health systems, payers and prescribers. The results of the study will be used to provide evidence of the effectiveness of tiotropium as add-on therapy in reducing exacerbations, reducing the increased dosing of current medications and health care resource utilization for their asthma patients.

In September 2015, the FDA approved Spiriva Respimat for Inhalation Spray for the long-term, once-daily, maintenance treatment of asthma in patients 12 years of age and older (6 years and above approved in Feb 2017).

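### Table 1 matches on neither reliever (SABA) fills nor LTRA use, so in Database I a symptomatic Tio patient without severe events can be paired with a more stable NonTio patient

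*Combined protocol and SAP*

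**What the plan says.** Section 9.3.3 makes a two-level control status a matching parameter. Under Table 1 a patient is "Well Controlled’ if patient has no prescriptions for an OCS, and no asthma-related emergency department visits or hospitalizations", with an exemption for events "other than the first diagnosis recorded in the data extracted". A further row covers only the other level: those patients "will further be matched based on the presence of asthma-related admissions, outpatient visits, and ER visits or use of OCS" in the pre-index period.

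The remaining rows apply to both levels of control. They are starting dose ("The dose level of the first prescription on the ICS/LABAI date (low, medium, or high"), age, gender, region, Charlson index, named comorbidities and a medication row ("Polypharmacy level matched within a range of 2 drugs"). Eosinophils and the Asthma Control Test (ACT) are matched in Database II only, where available.

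Section 9.12 expects channeling: patients given Tio "are likely to be less well-controlled and more severe both at baseline and during the follow up period". It offers two mitigations, the comparator definition and propensity score matching on control and severity. Among the matching variables it attributes to Table 1 is the number of prescriptions, both overall and for asthma medications. Table 1 has no asthma-medication count.

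Section 7 lists, among the guideline options for uncontrolled asthma, "other add-on therapy, including leukotriene receptor antagonists (LTRA), antibody biologics or oral corticosteroids". LTRA use is not named in Table 1, and reliever use is not mentioned anywhere in the protocol.

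**The concern.** The control variable registers severe events only. A patient who refills a reliever often, or who already takes an LTRA as an extra controller, is Well Controlled if there was no OCS prescription, ED visit or admission. If such patients are more common in the Tio group, control status can look balanced after matching while symptom burden is not.

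The primary hazard ratio would then carry confounding against Tio, which is the direction section 9.12 anticipates. The safeguard in section 9.7.1 adds a covariate to the Cox model only when a baseline characteristic is seen to be unbalanced, so it cannot act on a variable that is never tabulated.

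**Working it through.** **Step 1. What separates two Well Controlled patients in Database I.** Going through Table 1:

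- OCS, ED visits and admissions: absent by definition, apart from the first-diagnosis exemption.
- Asthma-related outpatient visits: matched only for Not Well Controlled patients. This is the main item that the restriction drops.
- ACT and eosinophils: not available in Database I.
- Polypharmacy: read as a count of drugs, it does not tell one reliever fill from ten. An LTRA adds one drug to a band that spans several.
- Starting dose, demographics, Charlson index and comorbidities: matched, but none measures current symptoms.

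**Step 2. How much of the cohort lacks a symptom measure.** The documents do not give the split. Section 9.4 gives about 690,000 claims-linked lives in Database II (within more than 20 million EMR) and about 150 million lives in Database I. Most matched patients probably come from Database I, but that is an inference.

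**Step 3. Where the contrast is sharpest.** Section 9.1 ties the NonTio entry route to starting dose:

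| Starting dose | How a patient enters NonTio |
|---|---|
| Low | Step-up to medium or high |
| Medium | Step-up to high |
| High | Additional prescription or refill of high dose |

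Starting dose is a matching parameter. High-dose Tio patients are therefore compared mainly with refillers, and low- or medium-dose Tio patients mainly with patients who also stepped up. A propensity score does not force exact agreement on dose, so this is a tendency. Section 9.9 concedes the high-dose mismatch as a limitation.

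**Step 4. Section 9.12 against Table 1.** Section 9.12 claims a match on asthma-related prescription counts and Table 1 does not contain one. Even if it did, a single count would add controllers to relievers, so a regular controller user and a heavy reliever user could score the same.

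**Step 5. Illustrative size.** The effect assumed in section 9.5 is a hazard ratio of 0.80: 0.0096/0.012 = 0.80 and 0.0224/0.028 = 0.80. The documents give neither the prevalence of reliever use nor its link to exacerbation, so every input below is assumed. Let a and b be the proportions with high reliever use in Tio and NonTio within the affected stratum, and r the hazard ratio for such use. Approximately,

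bias factor B = [1 + a(r − 1)] / [1 + b(r − 1)].

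| a | b | r | B | 0.80 would read |
|---|---|---|---|---|
| 0.40 | 0.25 | 1.5 | 1.200/1.125 = 1.067 | 0.853 |
| 0.40 | 0.25 | 2.0 | 1.40/1.25 = 1.120 | 0.896 |
| 0.40 | 0.30 | 1.5 | 1.20/1.15 = 1.043 | 0.835 |
| 0.60 | 0.20 | 2.5 | 1.90/1.30 = 1.462 | 1.169 |

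These values hold within the stratum only. If the stratum carried half the information (also assumed), the pooled value on the log scale would be 0.80 × B^0.5. The first two rows then give 0.826 and 0.847, and the last two give 0.817 and 0.967.

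**The case against.** There is a fair case that matching is better than the control definition alone suggests.

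- Section 9.12 commits to matching on asthma-related prescriptions, which on a plain reading would include SABA and LTRA fills. This stands as evidence of intent. It does not settle the matter, because the table it points to lacks the variable.
- A reader might infer that only Not Well Controlled patients receive any further matching. The documents do not support that. One row is restricted, and for Well Controlled patients most of its content is empty by definition. All other rows apply to everyone, including ACT and eosinophils in Database II where available.
- A reader might infer that Tio patients in general are compared with stable refillers. Refilling is one of three NonTio routes, and starting dose is matched.
- A reader might infer that the section 9.7.1 adjustment can never respond. Section 9.3.3 also records baseline exacerbation rate, resource use and cost. Section 9.3.2.1 counts a recorded exacerbation diagnosis without requiring an ED visit or admission. If that definition is used at baseline, some symptomatic Well Controlled patients would show up and could trigger adjustment. This stands: part of the gap may be caught indirectly.
- The control definition comes from a cited publication, and section 9.4 leaves covariate inclusion open until the data have been evaluated. That leaves room to add the variables. It is not a reason to omit them.

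**Conclusion.** The gap is real and limited in scope. Neither SABA fills nor LTRA use enters the control definition or any other Table 1 row, and section 9.12 describes an asthma-medication match that Table 1 does not provide. In Database I this leaves Well Controlled patients without a direct symptom measure, most consequentially among high-dose starters. Confounding against Tio is plausible there, given the direction of channeling that section 9.12 itself expects.

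It would go too far to say that the primary hazard ratio is biased by a known amount. A shift from 0.80 to 0.85–0.90 rests on assumed prevalences and an assumed risk ratio, and it applies to a stratum whose share of the cohort is not given. Other assumptions give 0.83 to 1.17 within the stratum. The change is worth making because it is cheap and bears on the mitigation the design relies on.

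**What to change.** Reconcile section 9.12 with Table 1 through these changes:

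1. Add the pre-index SABA fill count and LTRA use (yes/no) to Table 1 as matching parameters for all patients in both databases. Fix any SABA categories before outcomes are examined.
2. Apply the asthma-related outpatient-visit parameter to all patients, not only those Not Well Controlled.
3. List all three in the balance table before and after matching, so that the section 9.7.1 adjustment rule covers them.
4. Align the wording of section 9.12 with the revised table.

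The two medication variables come from pharmacy claims that section 9.4 already plans to use, at least for Database I, so no new source is needed there. The cost is slightly harder matching and a few more unmatched Tio patients, who are excluded under section 9.11.
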